# 6.6.3 Halfway between Surgery 1 and Surgery 2 (mid-point to be based on planned removal/replacement date +/- 1 week)

Patients will be asked to complete CASSETTE (Oncology) Patient In-Situ Questionnaire - Halfway\* questionnaire online, or if completed on paper, the questionnaires will be returned to the site team using a freepost envelope.

\*Oncology in situ (Halfway) questionnaire includes:

- Antibiotics/Hospitalisation
- Short Version Stent Quality of Life
- EQ-5D-5L
- Ureteric Stent Symptoms Questionnaire (with a stent in place) [USSQ]

The site research team will also contact the patient by telephone to collect any AEs/DDs as appropriate. Sites can also collect the questionnaires over the phone with the participant at this time point, if the participant choses this option.

#### 6.6.4 Within 24hrs prior to Surgery 2

Patients will be asked to complete CASSETTE (Oncology) Patient In-Situ Questionnaire - Surgery 2\* questionnaire online, or if completed on paper, the participants should bring the questionnaires with them to the day of removal surgery. (Sites can also collect questionnaires over the phone with the participant if the participant choses this option)

\*Oncology in situ (Surgery 2) questionnaire includes:

- Antibiotics/Hospitalisation
- Short Version Stent Quality of Life
- EQ-5D-5L
- Ureteric Stent Symptoms Questionnaire (with a stent in place) [USSQ]

## 6.6.5 Day of Surgery 2

The clinical team performs surgery and removes the novel ureteric stent (a standard of care ureteric stent may be replaced during this surgery as required). For oncology patients, this will take place approximately 25 weeks after insertion. The novel ureteric stents can be removed earlier if deemed necessary by the treating clinician. The novel ureteric stents can be removed earlier if deemed necessary by the treating clinician. At this stage, the clinical team will collect information relating to any adverse events and device deficiencies and record these on the database.

The clinical team will collect a urine sample and the experimental (novel) ureteric stent following the

procedures detailed in the laboratory manual. These will be analysed. The clinical team will perform any standard of care procedures as required, including performing safety blood tests. These will be detailed in the patients' medical notes and will only be collected as part of the trial data if clinically relevant.

#### 6.6.6 Two to three (2-3) weeks post-Surgery 2

Patients will be asked to complete CASSETTE (Oncology) Patient Questionnaire – Post Surgery 2\* questionnaire online or if completed on paper, the questionnaires will be returned to the site team using a freepost envelope.

\*Oncology (post-Surgery 2) questionnaire includes:

- Antibiotics/Hospitalisation
- Short Version Stent Quality of Life
- EQ-5D-5L
- Ureteric Stent Symptoms Questionnaire (after stent removal) [USSQ]

The site research team will also contact the patient by telephone to collect any AEs/DDs as appropriate 1-3 weeks post-surgery 2. If the phone call is to happen at week 2 or 3, then sites can also collect the questionnaires over the phone with the participant if the participant choses this option.

#### 6.7 TRIAL PROCEDURES – QUALITATIVE INTERVIEWS

#### 6.7.1 Qualitative interviews - Clinician cohort

At least ten (until sample saturation), clinicians (Consultants (if doctors) or equivalent to senior staff nurse (band 6) and above) who have experience of managing patients with ureteric stents and have been involved in managing patients in this trial with the novel ureteric stents, or those who may be interested in using the novel ureteric stent will initially be contacted by the CASSETTE Principal Investigators from each site to make them aware of the chance to participate in a qualitative interview and each clinician will be invited to email the CASSETTE study team to express their interest in participating. The CASSETTE study team will then share their details with the qualitative researcher at the University of Southampton. The qualitative researcher will invite clinicians to an interview (up to 45 minutes by telephone or video call). All clinicians will be given a copy of the clinician participant information sheet about these interviews. They will also be sent an email, a text and/or an invitation letter prior to their qualitative interview to remind them of their appointment if they wish to take part. The interviews with the clinicians will take place towards the last 3 months of the trial.

#### 6.7.2 Qualitative interviews – Patient cohort

Patients will have the option to consent to being contacted about taking part in the qualitative interviews, at the same time as consenting to the main trial. If they do not wish to take part in the main trial, they will still have the option to provide consent for their details to be shared with the qualitative researcher. The qualitative researcher (at the University of Southampton) will contact the patients who consented to their contact details being shared and discuss any potential questions and to arrange a time to speak with them by telephone or video call. They will also be sent an email, a text, and/or an invitation letter prior to their qualitative interview to remind them of their appointment. The interviews with participants will take place after their stent has been removed and the completion of the follow-up questionnaire.

#### 6.7.3 Qualitative interviews – Consent

During the telephone or video call, the qualitative researcher will check if the patient/clinician has read the Patient/Clinician Information Sheet, whether they understood it and whether they have any questions. They will then proceed to take verbal consent for participation in the qualitative interview study over the telephone or video call. The researcher will read out the consent questions included in the Interview Guide over the telephone or video call so that the patient/clinician can give verbal consent if they wish the interview to proceed. The verbal consent will be digitally recorded and stored securely. Patients/clinicians

CTU/FORM/5321 – Clinical Investigation Plan template for Clinical Investigations of Medical Devices (excl. IVDD) Version 1 14-DEC-2023 will be given a free choice and will be free to withdraw consent at any time. If the patient does not give consent for recording of consent and the subsequent interview, consent will not be collected, and this will be recorded as a screen failure for the qualitative sub-study.

#### 6.7.4 Qualitative interview conduct

The interviews with all participants will take place via telephone or video call, but the recording of the interviews will be online using a web-conference recorder (e.g. MS Teams) or on a physical recorder. The interviews, which will be up to 45 minutes in duration, will be semi-structured following an interview guide (see interview guide); this will enable topics crucial to the research to be covered whilst also providing the flexibility for participants to introduce pertinent issues.

The patients will be asked about their experiences of having a ureteric stent and complications which they experienced. If patients mention any issues that have not previously been recorded as adverse events or device deficiencies, these will be recorded in the database as per section 7 of this CIP.

Clinicians will be asked about their experiences of managing patients with ureteric stents. If the clinician mentions any issues with the device or instructions or surgery, these will have to be collected as adverse events or device deficiencies (please refer to section 7.2.2 of the CIP).

If the patient or the clinical interviewee mentions any information which the interview suspects to be related to adverse events or device deficiencies during the interview, the medically qualified interviewer will review the transcript from the interview and they will also provide the relevant site PI with the transcript from the interview for the clinician to confirm the adverse event or the device deficiency. If confirmed, the relevant site PI will need to check the database to see if the mentioned events have been recorded. If the relevant site PI confirms the adverse event or device deficiency which previously has not been recorded, then the interviewer will ask the patient or the clinical interviewee for the start and end date and the outcome of the event was. The interviewer will then need to send this information, via email to the relevant site staff, copying the CASSETTE trial inbox into the correspondence so that the CASSETTE trial team can follow this up.

Participants (both clinicians and patients) in the interview will receive a voucher worth £10 to thank them for their time.

The consent forms and audio-recordings will be stored until the end of the CASSETTE study and then destroyed as per UKDS recommendations (https://www.ukdataservice.ac.uk/manage-data/store/disposal). Although the digital recordings are not encrypted, measure will be taken to ensure the information remains secure. The qualitative researcher will keep the device in a locked drawer or secure place when not in use. Only the researcher or study team will have access to the locked drawer or cupboard. The recording will be uploaded at the first opportunity, and then the recording will be deleted from the device. Trial ID's will be assigned to those who consented to the main part and the qualitative sub study. For those participants who are only taking part in the qualitative sub study, a screening ID should be used. A participant identifier code is applied to each audio file captured. A member of staff will also obtain written consent for your contact details to be passed onto the qualitative researcher and the consent forms will be submitted to the CASSETTE study team via SafeSend. All data including personal identifiable information will be stored in a secure folder on the University of Southampton server and will only be accessible to members of the research team from University of Southampton.

#### 6.8 TRIAL INTERVENTION DISCONTINUATION AND PARTICIPANT WITHDRAWAL

Participants may withdraw voluntarily from the trial, or the Principal Investigator/Treating Healthcare Provider may discontinue a participant from the trial treatment for appropriate medical reasons.

#### **6.8.1** Discontinuation of Trial Intervention

#### a) Early stent removal

- If any clinical adverse event (AE), laboratory abnormality, or other medical condition or situation occurs such that continued participation in the trial would not be in the best interest of the participant
- Disease progression or other clinical situation such that continued participation in the trial would not be in the best interest of the participant

#### b) Discontinuation of trial intervention, but not suitable for removal

- If the participant develops an exclusion criterion that makes the change/removal of their stent unnecessary or inappropriate (either newly developed or not previously recognized) that precludes further trial participation
  - a. Expected survival <4 months
  - b. Unfit for stent removal/change
  - c. Unable to comply with study processes
- Participant unable to receive trial intervention within a defined time period by clinicians on case-by-case basis.

While pregnancy prior to stent insertion is an exclusion criteria, if a participant becomes pregnant after stent insertion, they will be followed up by the relevant clinician and remain in the trial.

The data to be collected at the time of trial intervention discontinuation will include the reason for discontinuation. Early removal which is due to the participant no longer needing the stent will be deemed as a success factor for the study. Where early removal is due to complications/symptoms, then clinical data will be collected on an eCRF in the trial database. In all cases, full details of the reason for trial intervention discontinuation should be recorded in the eCRF and participant's medical record.

#### 6.8.2 Trial Withdrawal

The participant is free to withdraw consent from the trial at any time, without providing a reason, and without their medical care or legal rights being adversely affected. If a patient withdraws before having their stent inserted, or if a stent is not inserted due to a clinical decision, then they will be replaced. Similarly, if a patient's stent is removed at any other hospital other than UCLH, or UHS then the participant will also be replaced.

Investigators should explain to participants the value of remaining in trial follow-up and allowing this data to be used for trial purposes. Where possible, participants who have withdrawn from the trial intervention should continue with relevant trial-associated processes as per the Schedule of Observations and Procedures. If participants additionally withdraw consent for this, they should revert to standard clinical care/follow-up as deemed by the responsible clinician. It would remain useful for the trial team to continue to collect any routine data (i.e., data that can be collected with no impact on the participant beyond standard clinical care/follow-up), and this will continue unless the participant explicitly requests otherwise. If this is requested, this constitutes complete withdrawal from the trial and should be recorded as end of study for the participant in the relevant eCRF and in their medical record, and no further data should be collected for this participant.

Patients who withdraw (or are withdrawn from the trial) may continue to consent and participate in the qualitative interviews if they wish, regardless of their level of withdrawal or the duration of their trial participation.

#### 6.9 STORAGE AND ANALYSIS OF CLINICAL SAMPLES

Procedures for dealing with urine samples and removed ureteric stents (collection, transport, analysis, storage, and destruction) are detailed in the Laboratory Manual. Samples will be destroyed following analysis, as per local standard procedures.

#### 6.10 DEFINITION OF END OF TRIAL

The end of trial is defined as the date when database has been frozen following the resolution of data queries, as far as possible, as agreed by the Trial Management Group.

## **7** SAFETY

#### 7.1 **DEFINITIONS**

Standard BS EN ISO 14155:2020 (in combination with the UK Medical Device Regulations 2002, as amended) provides the following definitions relating to adverse events in medical device trials:

Device deficiency	Inadequacy of an investigational medical device related to its identity, quality, durability, reliability, safety or performance. This may include malfunctions  , use error  , or inadequacy in the information supplied by the manufacturer.  Device deficiencies include malfunctions, use errors, and inadequacy in the information supplied by the manufacturer including labelling. These include deficiencies related to both the investigational medical device, or the comparator
Serious health threat	Signal from any adverse event or device deficiency that indicates an imminent risk of death or a serious deterioration in the health of subjects, users, or other persons, and that requires prompt remedial action for other subjects, users, or other persons  This would include events that are of significant and unexpected nature, such that they become alarming as a potential serious health hazard or possibility of multiple deaths occurring at short intervals
Adverse Event (AE)	Any untoward medical occurrence, unintended disease or injury or any untoward clinical signs (including an abnormal laboratory finding) in subjects, users or other persons whether or not related to the investigational medical device (and whether anticipated or unanticipated).  This includes events related to the investigational medical device or comparator. For subjects, this includes events related to all procedures involved. For users or other persons, this is restricted to events related to the use of investigational medical devices or comparators.
Serious Adverse Event (SAE)	Any adverse event which:  Results in death  Is life threatening  Requires hospitalisation or prolongation of existing hospitalisation  Results in persistent or significant disability or incapacity; or  Requires medical or surgical intervention to prevent a lifethreatening illness or injury, or persistent or significant disability or incapacity  Foetal distress, foetal death, a congenital abnormality, or birth defect including physical or mental impairment; or  Is otherwise considered medically significant by the investigator

	Planned hospitalisation for a pre-existing condition, or a procedure required by the Clinical Investigation Plan (Study Protocol) without serious deterioration in health, is not considered a serious adverse event
Adverse Device Effect (ADE)	Adverse event related to the use of an investigational medical device.  This includes any adverse event resulting from insufficient or inadequate instructions for use, deployment, implantation, installation, or operation; or any malfunction of the investigational medical device. This includes any event resulting from use error or from intentional misuse of the investigational medical device. This includes the comparator, where the comparator is also a medical device.
Serious Adverse Device Effect (SADE)	Adverse device effect that has resulted in any of the consequences characteristic of a serious adverse event.
Anticipated Serious Adverse Device Effect (ASADE)	Serious adverse device effect (SADE) which by its nature, incidence, severity, or outcome has been identified in the current risk assessment.
Unanticipated Serious Adverse Device Effect (USADE)	Serious adverse device effect (SADE) which by its nature, incidence, severity, or outcome has not been identified in the current risk assessment.

- 1. failure of an investigational medical device to perform in accordance with its intended purpose when used in accordance with the IFU, CIP, or IB
- 2. user action or lack of user action while using the medical device that leads to a different result than that intended by the manufacturer or expected by the user:
  - a. includes the inability of the user to complete a task
  - b. users may or may not be aware that a use error has occurred

#### 7.2 TRIAL SPECIFIC REQUIREMENTS

#### 7.2.1 Adverse Events

All Adverse Events (AEs) that are related to the experimental stent, or that relate to the medical condition requiring the stent should be reported on the Adverse Event eCRF. Reporting period starts from date of day of insertion of novel ureteric stent (Surgery 1) up until the date of the return of the last questionnaire, the date of the follow up phone call, or the date of the qualitative interview for patients that consent to the qualitative sub-study, whichever is the later.

#### 7.2.2 Device Deficiencies

Device deficiencies occurring between receipt at site and prior to their selection for insertion in a participant, should follow the procedures detailed in the CASSETTE Device Accountability document. Device deficiencies occurring after the device is selected for insertion in a participant (whether inserted or not) will be collected on the device deficiency (e)CRF for that specific participant.

Additionally, trial clinicians will assess whether or not these *might* have led to an SAE if:

- i. suitable actions had not been taken, or
- ii. intervention had not been made, or

#### iii. if circumstances had been less fortunate

If the device deficiency fulfils the reportable criteria above, then the event will also be reported to SCTU using the Serious Adverse Event Report Form for assessment and onward reporting as appropriate.

#### 7.2.3 Seriousness

A complete assessment of the seriousness must always be assessed by a medically qualified doctor who is registered on the delegation of responsibility log; this is usually the investigator.

All reportable adverse events that fulfil the criteria definition of 'serious' in CIP section 7.1, must be reported to SCTU using the Serious Adverse Event Report Form. Specific exceptions to this (as listed below) should be recorded as AEs rather than SAEs.

## 7.2.4 Exceptions:

For the purposes of this trial, the following **SAEs do not** require reporting to SCTU using the Serious Adverse Event Report Form:

• Hospitalisations for elective treatment of a pre-existing condition (the pre-existing condition needs to have been captured within the medical history CRF and/or the patient's medical notes).

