#### 5.3 INCLUSION CRITERIA

- 1. Aged 18 years or over
- 2. Ureteric stents clinically indicated either due to kidney stones or abdominal/pelvic cancers compressing ureters
- 3. Previous lived experience with ureteric stents

should inform the patients new healthcare professional.

- 4. Awaiting insersion/replacement of stents
- 5. Ability to give consent
- 6. Ability to interact with online and written study documentation
- 7. Sufficient English to complete study documentation and questionnaires

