## 7.5.2 Pre-existing Conditions

- Pre-existing conditions (prior to informed consent) should not be reported as an AE unless the conditions worsen during the trial. Instead, they will need to be recorded on the Medical History eCRF, within the trial database.

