## 7.6.3 Independent clinical reviewer

The delegated clinical reviewer is responsible for the below tasks. The Principal Investigator for each site will have the responsibility of clinically reviewing and providing a second opinion on all SAE's that occur at each other's site.

- 1. Using medical judgement in assigning the SAEs seriousness, causality and whether, if requested, the event was anticipated (in line with the expectedness information) where it is required as a second clinical opinion or if it has not been possible to obtain local medical assessment.
- 2. Immediate review of all USADEs
- 3. Review of specific SAEs and related SAEs in accordance with the trial risk assessment and CIP as detailed in the Trial Monitoring Plan.

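### The SAE exception in 7.2.4 is looser than the definition in 7.1, so an electively booked admission attributed to worsening of the underlying obstruction can stay off the SAE form

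*Protocol*

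**What the plan says.** Protocol section 7.1 makes hospital admission a seriousness criterion ("Requires hospitalisation or prolongation of existing hospitalisation") and then excludes one class of admission from SAEs altogether: "Planned hospitalisation for a pre-existing condition, or a procedure required by the Clinical Investigation Plan (Study Protocol) without serious deterioration in health".

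Section 7.2.4 adds a trial-specific exception. It lists SAEs that need no SAE report form, and its single entry is "Hospitalisations for elective treatment of a pre-existing condition". The only condition attached is that "the pre-existing condition needs to have been captured within the medical history CRF and/or the patient's medical notes". Section 7.2.3 gives the consequence: "Specific exceptions to this (as listed below) should be recorded as AEs rather than SAEs".

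Three other provisions set the reach of the exception:

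- Section 7.2.1 limits AE reporting to events related to the experimental stent or to the medical condition for which it is needed.
- Section 5.3, inclusion criterion 2, requires "Ureteric stents clinically indicated either due to kidney stones or abdominal/pelvic cancers compressing ureters", so every participant enters with a qualifying pre-existing condition.
- Section 7.5.2 dates pre-existing conditions to before informed consent and says that they "should not be reported as an AE unless the conditions worsen during the trial".

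**The concern.** The definition and the exception should cover the same admissions, and on their wording they do not. The exception replaces *planned* with *elective*, carries no qualifier about deterioration, and says nothing about admissions that may be due to the device. Its documentation condition screens out little, because the stone disease or compressing cancer will be in every participant's notes.

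What is at stake is the level of scrutiny. An exempt event is kept as an AE but gets no SAE form. It is then outside the arrangement in section 7.6.3, under which each site's Principal Investigator is responsible for "providing a second opinion on all SAE's that occur at each other's site", and outside the reporting of SAEs to the MHRA in section 7.5.1.3. In a first-in-human device study, whether a worsening obstruction comes from the disease or from the stent is exactly the judgement that benefits from a second reader. As written, whether that reader sees the case could depend on how the admission was booked.

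**Working it through.** No figure is involved, so the check sets the passages side by side.

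**Step 1: compare the two exclusions.**

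| Feature | 7.1 (not an SAE) | 7.2.4 (SAE, but no SAE form) |
|---|---|---|
| Type of admission | Planned | For elective treatment |
| Deterioration qualifier | Present; reach unclear | Absent |
| Documentation condition | None | Medical history CRF and/or notes |
| Device-related admissions carved out | Not stated | Not stated |

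In 7.1 no comma precedes the words about deterioration. They may qualify both the planned hospitalisation and the CIP procedure, or the procedure alone. On the first reading 7.2.4 is looser in two respects. On the second, the gap is *planned* against *elective* only. That still matters, because an elective admission can first be arranged during the trial. Neither section says by what date an admission must have been planned.

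**Step 2: ask what 7.2.4 can act on.** Admissions excluded by 7.1 are not SAEs at all. Section 7.2.4 introduces its list as SAEs. Read literally, it therefore has effect only on admissions that 7.1 has not already removed, which are those that were not planned or, on the first reading, that involved serious deterioration.

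**Step 3: ask which conditions it reaches.** Elective care for an unrelated condition is already outside reporting under 7.2.1. Among reportable events, the pre-existing condition most directly reached is the stone disease or ureteric compression.

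**Step 4: trace two cases.**

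- *Study stent recognised as failing to drain.* Section 7.4.1 lists this as a device deficiency. Section 7.2.2 has clinicians assess whether it might have led to an SAE without intervention. If so, it goes on the SAE form and, under 7.5.1.3, to the MHRA. Section 7.2.4 does not switch this route off. The case is covered.
- *Worsening hydronephrosis or kidney injury attributed to tumour or stone, admission first arranged during the trial and booked electively, no device deficiency identified.* Section 7.5.2 makes the worsening reportable as an AE. The admission makes it serious under 7.1. Section 7.2.4 then removes the SAE form, and 7.2.2 does not apply. The event stays an AE.

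**Step 5: compare the second case with the endpoint.** In section 2.2, component (b) of stent failure is limited to stent-related intervention, but component (c), kidney failure and/or worsening hydronephrosis, carries no such limit. The second case can therefore count as a primary-endpoint failure while being exempt from the SAE form.

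**The case against.** A reader might infer that readmissions to change or bypass a failing study stent escape SAE reporting generally. The documents do not support that. The stent is inserted after consent, so its failure is not a pre-existing condition in the sense of 7.5.2, and the device-deficiency route leads to the SAE form and the MHRA. For such an event to be missed, a medically qualified assessor would have to treat it as care of the underlying disease and also leave 7.2.2 and 7.4.1 unapplied.

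It can also be said that 7.2.4 was probably meant as a loose restatement of 7.1, and that the event is not lost. It is recorded as an AE and, where it qualifies, as a primary-endpoint event. Section 6.8.1 requires full reasons for any early discontinuation. Section 1.2.5 has functional failure needing intervention investigated under the stop/go criteria. The DSMC monitors the main outcome measures (section 12.2). The exception also covers hospitalisations only, so an event that is serious on another 7.1 criterion arguably remains reportable.

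All of this stands, and it narrows the point. It does not close it. The deficiency route starts only once someone judges the device inadequate, and in the exposed case that judgement has gone the other way. Section 1.2.2 itself calls for clinical judgement on each encrustation event, and section 7.3 classes a relationship that cannot be assessed as possible, which would make a serious event an anticipated or unanticipated serious adverse device effect. An AE record does not bring the second opinion or the MHRA report that would test the attribution.

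**Conclusion.** The point holds in a limited form. Sections 7.1 and 7.2.4 do not match, and the exception is the looser of the two. The gap covers admissions first arranged during the trial, booked electively, and attributed to worsening of the underlying obstruction with no device deficiency identified. Followed as written, such an event is recorded only as an AE and misses both the cross-site second opinion and the MHRA report.

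The size cannot be estimated. The protocol gives no expected failure rate, no share of admissions booked electively and no indication of how often worsening would be attributed to disease; the count could be zero. The conclusion rests on a literal reading of 7.2.4 and on taking *planned* in 7.1 to mean arranged beforehand. It does not depend on how the deterioration qualifier in 7.1 is read; that reading only decides whether the gap has one part or two. This is a safety-reporting point with no effect on the sample size or the primary estimate. It is worth correcting because deciding between disease and device is an open question in this study and the correction is small.

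**What to change.** Reconcile 7.2.4 with 7.1 in one sentence. Limit the exception to hospitalisations already planned before informed consent (which would match 7.5.2) or before Surgery 1, and without serious deterioration in health. State that it does not cover an admission for an event meeting any component of the primary endpoint in section 2.2. Reword 7.1 at the same time, so that it is clear whether the deterioration qualifier applies to planned hospitalisations as well as to CIP procedures. Carry the change into the reporting flowchart mentioned in 7.5.

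The cost is a short CIP amendment and a few more SAE forms, some of which will prove to be disease-related. No analysis changes.
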